### Table of Study Procedures (1/4)

Phase III Trial, Group 1 (Mexico): 6 Visits, 4 Vaccination Visits, 4 Telephone Calls, 3 Blood Samples, 11 Months Duration Per Subject for Subjects Randomized to Receive MenACYW Conjugate Vaccine

Visit / Telephone Call	Visit 1	TC1*	Visit 2	Visit 3	TC2*	Visit 4	TC3†	Visit 5	TC4*	Visit 6
Approximate Subject Age	2 months‡	-	4 months	6 months	-	7 months	-	12 months	-	13 months
Trial timelines (days, months)	D0	V01 +8 days	V01 + 60 days	V02 + 60 days	V03 + 8 days	V03 + 30 days	V05 -14 days	V04 +5 months	V05 +8 days	V05 + 30 days
Time windows (days)	NA	+2 days	+14 days	+14 days	+2 days	+14 days	+2 days	+14 days	+2 days	+14 days
Informed consent form signed and dated	X									
Inclusion/exclusion criteria	X									
Collection of demographic data	X									
Medical history§ (including history of maternal immunization against tetanus)	X									
Physical examination and temperature	X**		X††	X††				X††		
Review of temporary contraindications for blood sampling (BL) ‡‡§§	X					X				X
BL (6 mL)	BL0001					BL0002				BL0003
Review of warnings and precautions and / or contraindications for vaccinations	X		X	X				X		
Review conditions for withdrawal***	X		X	X				X		
Contact IRT system for randomization / allocation of subject number / vaccine assignment	X									
Contact IRT system for vaccine dose number for all vaccines to be given			X	X				X		
Vaccination with MenACYW conjugate vaccine	X			X				X		
Prevnar 13® vaccination†††	X		X	X				X		

Visit / Telephone Call	Visit 1	TC1*	Visit 2	Visit 3	TC2*	Visit 4	TC3†	Visit 5	TC4*	Visit 6
Approximate Subject Age	2 months‡	-	4 months	6 months	-	7 months	-	12 months	-	13 months
RotaTeq® vaccination†††	X		X	X						
Hexacima® vaccination†††	X		X	X				X		
M-M-R®II vaccinations†††								X		
Immediate surveillance (30 min)	X		X	X				X		
Diary Card (DC):										
Provided	DC1		DC2	DC3		DC4		DC5		
Reviewed			DC1	DC2		DC3		DC4		DC5
Collected			DC1	DC2		DC3		DC4		DC5
Telephone call		X			X		X		X	
Recording of solicited injection site and systemic reactions	X		X	X				X		
Recording of unsolicited AEs		Reported from D0 to D30 after each vaccination visit								
Reporting of SAEs / AESIs‡‡‡	To be reported throughout the study period									
Collection of reportable concomitant medications	To be reported throughout the study period									
Trial termination record										X

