### Table of Study Procedures (2/4)

Phase III Trial, Group 2 (Mexico): 6 Visits, 4 Vaccination Visits, 5 Telephone Calls, 3 Blood Samples, 11 Months Duration Per Subject for Subjects Randomized to Receive Menveo Vaccine

Visit / Telephone Call (TC)	Visit 1	TC1*	Visit 2	TC2*	Visit 3	TC3*	Visit 4	TC4†	Visit 5	TC5*	Visit 6
Approximate Subject Age	2 months‡	-	4 months	-	6 months	-	7 months	-	12 months	-	13 months
Trial timelines (days, months)	D0	V01 +8 days	V01+60 days	V02 +8 days	V02 +60 days	V03 +8 days	V03 +30 days	V05 -14 days	V04 +5 months	V05 +8 days	V05 +30 days
Time windows (days)	NA	+2 days	+14 days	+2 days	+14 days	+2 days	+14 days	+2 days	+14 days	+2 days	+14 days
Informed consent form signed and dated	X										
Inclusion/exclusion criteria	X										
Collection of demographic data	X										
Medical history§	X										
Physical examination and temperature	X**		X††		X††				X††		
Review of temporary contraindications for blood sampling (BL) ‡‡ §§	X						X				X
BL (6 mL)	BL0001						BL0002				BL0003
Review of warnings and precautions and / or contraindications for vaccinations	X		X		X				X		
Review conditions for withdrawal***	X		X		X				X		
Contact IRT system for randomization / allocation of subject number / vaccine assignment	X										
Contact IRT system for vaccine dose number for all vaccines to be given			X		X				X		
Vaccination with Menveo®	X		X		X				X		

Visit / Telephone Call (TC)	Visit 1	TC1*	Visit 2	TC2*	Visit 3	TC3*	Visit 4	TC4†	Visit 5	TC5*	Visit 6
Approximate Subject Age	2 months‡	-	4 months	-	6 months	-	7 months	-	12 months	-	13 months
Prevnar 13® vaccination†††	X		X		X				X		
RotaTeq® vaccination†††	X		X		X						
Hexacima® vaccination†††	X		X		X				X		
M-M-R®II vaccinations†††									X		
Immediate surveillance (30 min)	X		X		X				X		
Diary Card (DC):											
Provided	DC1		DC2		DC3		DC4		DC5		
Reviewed			DC1		DC2		DC3		DC4		DC5
Collected			DC1		DC2		DC3		DC4		DC5
Telephone call		X		X		X		X		X	
Recording of solicited injection site and systemic reactions	X		X		X				X		
Recording of unsolicited AEs	Collected from D0 to D30 after each vaccination visit										
Reporting of SAEs / AESIs§§§	To be reported throughout the study period										
Collection of reportable concomitant medications	To be reported throughout the study period										
Trial termination record											X

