### ***Collection of Safety Data***

All subjects will be followed for safety from Visit 1 to the last study visit.

- All subjects will be observed for 30 minutes after vaccination under the supervision of a responsible healthcare professional at each study site and any unsolicited systemic AEs occurring during that time will be recorded as immediate unsolicited systemic AEs in the electronic case report form (eCRF).
- The subject's parent / guardian will record information in a diary card about solicited injection-site reactions and solicited systemic reactions from D0 to D7 after each vaccination and unsolicited AEs will be recorded from D0 after each vaccination until the subject returns for the next study visit.
- Serious AEs (including AEs of special interest [AESIs]) will be recorded in a diary card throughout the study. The subject's parent / guardian will be asked to notify the site immediately about any potential SAEs at any time during the trial.
- A member of the study staff will contact subject's parent / guardian by telephone 8 days (+2 days) after each vaccination visit to identify the occurrence of any SAE (including AESIs) not yet reported and to remind them to complete the diary card after each vaccination visit, and to bring it back to the next study visit.
- The completed diary cards will be collected and reviewed with the subject's parent / guardian at subsequent visits.
- A member of the study staff will contact the subject's parent / guardian by telephone 14 days (+2 days) before the first study visit of the subject's second year of life to identify the occurrence of any SAE not yet reported and to remind them to complete the diary card and to bring it back to the next study visit so it can be reviewed at the study site.

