***For subjects in Groups 1 and 2:***

- Prevnar 13®: inject IM into the anterolateral area of the thigh (preferably the left thigh).

---

a The only other vaccine that can be administered with the meningococcal vaccine in the right thigh is ENGERIX-B®. Do not administer Pentaxim® or PREVNAR 13® in the right thigh.

b Multiple injections given in the same extremity should be separated as far as possible preferably 2.54 cm to 3.81 cm apart with a minimum of 2.54 cm. Keep the subject under observation for 30 minutes and record any adverse reaction (AR) in the source document.

- Hexacima®: inject IM into the anterolateral area of the thigh (preferably the left thigh).b
  - RotaTeq®: administer PO per instructions in the package insert.
- 7) Give the parent / guardian a diary card (DC2).
  - 8) Remind the parent / guardian to expect a telephone call 8 days after Visit 2 and to bring back the diary card when they return for Visit 3 at a specified date and time.
  - 9) Remind the parent / guardian to notify the site in case of an SAE.
  - 10) Complete the relevant CRFs for this visit.

Telephone Call 2 (Group 2) (8 [+2] days after Visit 2)

Refer to steps in Telephone Call 1.

Visit 3 (60 [+14] days after Visit 2): Collection of Safety Information and Vaccination

- 1) If the diary card information from D0 to D07 (DC2) has not yet been obtained, obtain it at this time. Collect and review the pages of the diary card with the parent / guardian, including any AEs, medications, or therapy that occurred since vaccination. If an SAE, including an AESI, has occurred, follow the instructions in [Section 10](#) for reporting it.
- 2) Review warnings and precautions to vaccinations.
- 3) Review contraindications to subsequent vaccinations.
- 4) Review conditions for withdrawal.
- 5) Contact IRT system for dose number for all vaccines to be given.
- 6) Administer the appropriate study vaccine per Operating Guidelines. Each vaccine should be administered in an assigned location and documented appropriately.
  - Meningococcal vaccine: inject IM into the anterolateral area of the thigh (preferably the right thigh).a,b
  - Hexacima®: inject IM into the anterolateral area of the thigh (preferably the left thigh).
  - Prevnar 13®: inject IM into the anterolateral area of the thigh (preferably the left thigh).b

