- A blood sample 30 days (+14 days) after the 2nd dose of MenACYW conjugate vaccine (Visit 5)
- A blood sample 30 days (+14 days) after the 3rd dose of MenACYW conjugate vaccine (Visit 7)

Group 4:

- A blood sample at baseline (before the first study vaccination, at Visit 0)
- A blood sample 30 days (+14 days) after the 1st dose of ENGERIX B[®] and 3rd dose of Pentaxim[®] vaccines (Visit 5)
- A blood sample 30 days (+14 days) after the 1st dose of MMR vaccine (Visit 7)

Collection of Safety Data

All subjects will be followed for safety from Visit 1 to the last study visit.

- All subjects will be observed for 30 minutes after vaccination under the supervision of a responsible healthcare professional at each study site and any unsolicited

systemic AEs occurring during that time will be recorded as immediate unsolicited systemic AEs in the electronic case report form (eCRF).

- The subject's parent / guardian will record information in a diary card about solicited injection-site reactions and solicited systemic reactions from D0 to D7 after each vaccination and unsolicited AEs will be recorded from D0 after each vaccination until the subject returns for the next study visit.
- Serious AEs (including AEs of special interest [AESIs]) will be recorded in a diary card throughout the study. The subject's parent / guardian will be asked to notify the site immediately about any potential SAEs at any time during the trial.
- A member of the study staff will contact subject's parent / guardian by telephone 8 days (+2 days) after each vaccination visit to identify the occurrence of any SAE (including AESIs) not yet reported and to remind them to complete the diary card after each vaccination visit, and to bring it back to the next study visit.
- The completed diary cards will be collected and reviewed with the subject's parent / guardian at subsequent visits.
- A member of the study staff will contact the subject's parent / guardian by telephone 14 days (+2 days) before the first study visit of the subject's second year of life to identify the occurrence of any SAE not yet reported and to remind them to complete the diary card and to bring it back to the next study visit so it can be reviewed at the study site.

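### In Mexico the day-8 safety call after Visit 2 is scheduled for Group 2 but not Group 1, although the text promises it to both arms

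*Protocol*

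**What the plan says.** Protocol 5.1.3 (Collection of Safety Data) states that parents will be contacted "by telephone 8 days (+2 days) after each vaccination visit". The synopsis and SAP 3.1 say the same, and none of the three limits the call to one arm. In Protocol 5.1.4 (Mexico), Visit 2 step 8 is likewise unrestricted: "Remind the parent / guardian to expect a telephone call 8 days after Visit 2".

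The schedules differ. The Table of Study Procedures (1/4) is headed "Phase III Trial, Group 1 (Mexico): 6 Visits, 4 Vaccination Visits, 4 Telephone Calls, 3 Blood Samples" and has no call between Visits 2 and 3. Table (2/4) is headed "Phase III Trial, Group 2 (Mexico): 6 Visits, 4 Vaccination Visits, 5 Telephone Calls, 3 Blood Samples" and places a call 8 days after Visit 2. SAP Tables 3.3 and 3.4 repeat these schedules. Section 5.1.4 labels the call after Visit 2 "Telephone Call 2 (Group 2) (8 [+2] days after Visit 2" and puts Group 1's second call after Visit 3.

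Visit 2 is a vaccination visit in both arms. Group 1 receives Prevnar 13, Hexacima and RotaTeq; Group 2 receives the same plus Menveo. Solicited-reaction recording is marked at Visit 2 for both.

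**The concern.** A site cannot follow both the text and the Group 1 schedule, and Group 1 parents are told to expect a call that their table does not contain. If sites follow the tables, two randomised arms receive different staff contact after the same visit.

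That matters because observational objective 1 sets Group 1 against Group 2 on safety, Protocol 5.1.2 describes the study as a pivotal safety study, and the trial is open-label. The call asks about SAEs and AESIs not yet reported, records health status and reminds parents to complete the diary. SafAS3 describes safety after Visit 2 for both arms, and the same events enter the any-dose tables.

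Diary completeness can reach the results. Under SAP 4.4.1.1.1, a solicited reaction other than fever that is marked as not present, with all daily records missing, is derived as none. Under SAP 4.4.1.1.3, a child with no non-missing presence for an endpoint leaves the analysis of that endpoint.

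**Working it through.** **Inputs.** Vaccination visits (1, 2, 3 and 5) and call timings come from the Tables of Study Procedures (1/4) and (2/4), checked against Protocol 5.1.4. Planned sizes are 200 in Group 1 and 100 in Group 2.

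| Contact | Group 1 | Group 2 |
|---|---|---|
| Day 8 after Visit 1 | TC1 | TC1 |
| Day 8 after Visit 2 | none | TC2 |
| Day 8 after Visit 3 | TC2 | TC3 |
| 14 days before Visit 5 | TC3 | TC4 |
| Day 8 after Visit 5 | TC4 | TC5 |

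**Reproducing the plan's own totals.** Calls per child = day-8 calls + the reminder before Visit 5.

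- Group 1: 3 + 1 = 4, as its table heading states.
- Group 2: 4 + 1 = 5, as its table heading states.

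**What the text requires.** One call after each of 4 vaccination visits, plus the reminder: 4 + 1 = 5 in each arm. Group 1 is one short, and the missing call is the one after Visit 2.

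**Coverage at planned enrolment.** Children × day-8 calls, over children × vaccination visits.

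- Group 1: 200 × 3 = 600 of 200 × 4 = 800, or 75%.
- Group 2: 100 × 4 = 400 of 100 × 4 = 400, or 100%.
- Shortfall in Group 1: 800 − 600 = 200 calls.

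**What is the same after Visit 2.** In both arms a diary card (DC2) is issued at Visit 2 and collected and reviewed at Visit 3; parents record solicited reactions on days 0 to 7; 30-minute surveillance is marked; and parents are reminded at Visit 2 to return the card and to notify the site of any SAE. What differs is the first scheduled staff contact after Visit 2: day 8 (+2) in Group 2, and Visit 3 at day 60 (+14) in Group 1.

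**Is it a meningococcal-dose rule?** Group 1 receives no meningococcal vaccine at Visit 2, so calls might have been tied to meningococcal doses. The Russian schedule does not bear this out: its first call follows Visit 1, where only Prevnar 13 is given, and Group 4 never receives a meningococcal vaccine yet has day-8 calls. Both Russian groups lack a call after their Visit 3, so the arms there are treated alike. Only the Mexican pair is unbalanced.

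**The case against.** The strongest reply is that the main safety collection is identical in the two arms and that the documents conflict rather than establish unequal treatment. Much of this stands.

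- A reader might infer that Group 1 depends on recall some 60 days later. It does not: parents complete a diary card as events occur, and Visit 3 reviews that record.
- A reader might infer that Group 1 has no prompt after this visit. It lacks only the telephone prompt; the diary and SAE reminders are given in person at Visit 2.
- The call falls on days 8 to 10, after the day 0 to 7 solicited window. It can prompt late completion of the card but does not act during daily recording.
- An SAE not raised at day 8 can still be reported by the parent or found at Visit 3, and SAP 4.4.1.3 analyses SAEs throughout the study. Earlier reporting alone need not change those tables.
- If sites followed the text and step 8, there was no imbalance.
- The SafAS3 contrast already differs by a Menveo dose, and safety is descriptive.

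What does not fall away is that both documents schedule one arm for an active query and diary reminder that the other is promised but not given. The extra Menveo dose makes this harder to interpret: an excess of events in Group 2 after Visit 2 could come from that dose, the extra call or both, and the planned tables cannot separate them.

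**Conclusion.** The inconsistency is established in both documents: 3 of 4 vaccination visits followed by a day-8 call in Group 1, against 4 of 4 in Group 2. It is confined to one staff call after one visit.

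Any effect on results is conditional. It needs sites to have followed the tables rather than the text, and the call to have brought out events or diary entries that the card and the Visit 3 review would otherwise have missed. If both hold, the plausible direction is fuller reporting in Group 2, which would make Group 1 look relatively better in the SafAS3 and any-dose tables. A reader might take a bias favouring the investigational vaccine as shown; the documents support neither its existence nor a size, and the direction is a reasoned expectation only. The coverage figures assume planned enrolment and attendance at every vaccination visit.

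**What to change.** Add the call 8 (+2) days after Visit 2 to the Group 1 Table of Study Procedures, to Protocol 5.1.4 and to SAP Table 3.3, so that they agree with Protocol 5.1.3, the synopsis, Visit 2 step 8 and SAP 3.1. The call total in the Group 1 headings becomes 5. The cost is about 200 short calls by existing staff, already promised in the text.

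This may come too late: Protocol 5.1.5 plans the end of inclusion for December 2020 and the end of study for January 2022, and SAP 5.7 is written partly in the past tense. For children already past Visit 2, use the telephone contact logs, which Protocol 13.2 lists as source documents, to establish whether Group 1 calls were made. Report call completion, and DC2 return and completion, by arm beside the SafAS3 and any-dose results for Groups 1 and 2. That costs a log check and one small table.

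An any-dose table with the Visit 2 period removed is not a substitute. It would drop a Menveo dose from Group 2 but no MenACYW dose from Group 1, changing the exposure compared, so it could not isolate the effect of the call. SafAS1, SafAS5 and SafAS6 already show the other vaccination visits separately.

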#### **5.1.4 Visit Procedures**

##### ***Mexico***

##### **Visit 1 (Day 0): Inclusion, Blood Sampling (BL), and Vaccination**

- 1) Give the parent / guardian information about the study, obtain written informed consent, and give him/her a signed copy.
- 2) Check inclusion and exclusion criteria for eligibility.
- 3) Collect demographic data.
- 4) Obtain verbal medical history about the subject, including ongoing medications and history of maternal immunization against tetanus.
- 5) Conduct a physical examination
- 6) Measure temperature. If the temperature is  $\geq 38^{\circ}\text{C}$ , postpone vaccination until the condition is resolved.
- 7) Contact IRT system for randomization / allocation of subject number / vaccine assignment

- 8) Review temporary contraindications for blood sampling. Ensure the subject has not had any antibiotics within the previous 72 hours (3 days).
- 9) Collect 6-mL blood sample (BL0001) (see [Section 7.1](#) for detailed instructions regarding the handling of blood samples). If attempts to obtain the first blood draw are unsuccessful (after reasonable attempts as per local regulations / practice), then Visit 1 can be rescheduled to a later date at which point inclusion/exclusion criteria must be re-validated. If the first blood draw cannot be obtained, the subject will be withdrawn from the study without being vaccinated
- 10) Review warnings and precautions to vaccinations.
- 11) Administer the appropriate study vaccines per Operating Guidelines. Each vaccine should be administered in an assigned location and documented appropriatelya.
  - Meningococcal vaccine: inject IM into the anterolateral area of the thigh (preferably the right thigh).b,c
  - Prevnar 13®: inject IM into the anterolateral thigh (preferably the left thigh).b
  - Hexacima®: inject IM into the anterolateral area of the thigh (preferably the left thigh).b
  - RotaTeq®: administer PO per instructions in the package insert.
- 12) Keep the subject under observation for 30 minutes and record any AE in the source document.
- 13) Give the parent / guardian a diary card (DC1), a thermometer, and a ruler, and go over the instructions for their use.
- 14) Remind the parent / guardian to expect a telephone call 8 days after Visit 1 and to bring back the diary card when they return for Visit 2 at a specified date and time.
- 15) Remind the parent / guardian to notify the site in case of an SAE.
- 16) Complete the CRFs for this visit.

---

a Failure to administer vaccines in the designated limb will not constitute a protocol deviation, but should be recorded as a comment in the CRF. If the initial vaccines are administered in the wrong limbs, this should be corrected for subsequent injections.

b The only other vaccine that can be administered with the meningococcal vaccine in the right thigh is ENGERIX-B®. Do not administer Pentaxim® or PREVNAR 13® in the right thigh.

c Multiple injections given in the same extremity should be separated as far as possible preferably 2.54 cm to 3.81 cm apart with a minimum of 2.54 cm. Keep the subject under observation for 30 minutes and record any AR in the source document.

Telephone Call 1 (8 [+2] days after Visit 1)

**Note:** If Day 8 falls on a weekend or a holiday, the telephone call may be made on the following business day.

- 1) Record relevant information concerning the subject's health status on the telephone contact form. If an SAE has occurred that has not yet been reported, follow the instructions in [Section 10](#) for reporting it.
- 2) Remind the parent / guardian to do the following:
  - Complete the D0 to D07 pages of the diary card.
  - Complete the remaining pages of the diary card, and bring them to the next visit.
  - Notify the site in case of an SAE.

Visit 2 (60 [+14] days after Visit 1): Collection of Safety Information and Vaccination

- 1) If the diary card information from D0 to D07 (DC1) has not yet been obtained, obtain it at this time. Collect and review the pages of the diary card with the parent / guardian, including any AEs, medications, or therapy that occurred since vaccination. If an SAE, including an AESI, has occurred, follow the instructions in [Section 10](#) for reporting it.
- 2) Review warnings and precautions to vaccinations.
- 3) Review contraindications to subsequent vaccinations.
- 4) Review conditions for withdrawal.
- 5) Contact IRT system for dose number for all vaccines to be given.
- 6) Administer the appropriate study vaccine per Operating Guidelines. Each vaccine should be administered in an assigned location and documented appropriately.

***For subjects in Group 2 only:***

- Meningococcal vaccine: inject IM into the anterolateral area of the thigh (preferably the right thigh).a,b

***For subjects in Groups 1 and 2:***

- Prevnar 13®: inject IM into the anterolateral area of the thigh (preferably the left thigh).

---

a The only other vaccine that can be administered with the meningococcal vaccine in the right thigh is ENGERIX-B®. Do not administer Pentaxim® or PREVNAR 13® in the right thigh.

b Multiple injections given in the same extremity should be separated as far as possible preferably 2.54 cm to 3.81 cm apart with a minimum of 2.54 cm. Keep the subject under observation for 30 minutes and record any adverse reaction (AR) in the source document.

- Hexacima®: inject IM into the anterolateral area of the thigh (preferably the left thigh).b
  - RotaTeq®: administer PO per instructions in the package insert.
- 7) Give the parent / guardian a diary card (DC2).
  - 8) Remind the parent / guardian to expect a telephone call 8 days after Visit 2 and to bring back the diary card when they return for Visit 3 at a specified date and time.
  - 9) Remind the parent / guardian to notify the site in case of an SAE.
  - 10) Complete the relevant CRFs for this visit.

Telephone Call 2 (Group 2) (8 [+2] days after Visit 2)

Refer to steps in Telephone Call 1.

Visit 3 (60 [+14] days after Visit 2): Collection of Safety Information and Vaccination

- 1) If the diary card information from D0 to D07 (DC2) has not yet been obtained, obtain it at this time. Collect and review the pages of the diary card with the parent / guardian, including any AEs, medications, or therapy that occurred since vaccination. If an SAE, including an AESI, has occurred, follow the instructions in [Section 10](#) for reporting it.
- 2) Review warnings and precautions to vaccinations.
- 3) Review contraindications to subsequent vaccinations.
- 4) Review conditions for withdrawal.
- 5) Contact IRT system for dose number for all vaccines to be given.
- 6) Administer the appropriate study vaccine per Operating Guidelines. Each vaccine should be administered in an assigned location and documented appropriately.
  - Meningococcal vaccine: inject IM into the anterolateral area of the thigh (preferably the right thigh).a,b
  - Hexacima®: inject IM into the anterolateral area of the thigh (preferably the left thigh).
  - Prevnar 13®: inject IM into the anterolateral area of the thigh (preferably the left thigh).b
  - RotaTeq®: administer PO per instructions in the package insert.

---

a The only other vaccine that can be administered with the meningococcal vaccine in the right thigh is ENGERIX-B®. Do not administer Pentaxim® or PREVNAR-13® in the right thigh.

b Multiple injections given in the same extremity should be separated as far as possible preferably 2.54 cm to 3.81 cm apart with a minimum of 2.54 cm. Keep the subject under observation for 30 minutes and record any AR in the source document.

- 7) Keep the subject under observation for 30 minutes and record any AE in the source document.
- 8) Give the parent / guardian a diary card (DC3).
- 9) Remind the parent / guardian to expect a telephone call 8 days after Visit 3 and to bring back the diary card when they return for Visit 4 at a specified date and time.
- 10) Remind the parent / guardian to notify the site in case of an SAE.
- 11) Complete the relevant CRFs for this visit.

Telephone Call 2 (Group 1) (8 [+2] days after Visit 3) / Telephone Call 3 (Group 2) (8 [+2] days after Visit 3)

Refer to steps in Telephone Call 1.

Visit 4 (30 [+14] days after Visit 3): Collection of Safety Information and Blood Sampling

- 1) If the diary card information from D0 to D07 (DC3) has not yet been obtained, obtain it at this time. Collect and review the pages of the diary card with the parent / guardian, including any AEs, medications, or therapy that occurred since vaccination. If an SAE, including an AESI, has occurred, follow the instructions in [Section 10](#) for reporting it.
- 2) Review temporary contraindications to blood sampling
- 3) Collect 6-mL blood sample (BL0002) (see [Section 7.1](#) for detailed instructions regarding the handling of blood samples).
- 4) Give the parent / guardian a diary card (DC4).
- 5) Remind the parent / guardian to bring back the diary card when they return for Visit 5 at a specified date and time.
- 6) Remind the parent / guardian to notify the site in case of an SAE.
- 7) Complete the relevant CRFs for this visit.

Telephone Call 3 (Group 1) (14 [+ 2] days before Visit 5) / Telephone Call 4 (Group 2) (14 [+ 2] days before Visit 5)

- 1) Contact the subjects' parent/ guardian by telephone within 14 days before V05 to remind them about the forthcoming study visit.
- 2) If the subject participation in the study is discontinued:
  - a. Review the diary card including any AEs, medications, or therapy that occurred since the last visit.
  - b. Ask the subject's parent / guardian if the subject has experienced any SAE in the time since vaccination that has not been reported to the study personnel. If an SAE, including an AESI, has occurred, follow the instructions in [Section 10](#) for reporting it.
  - c. Make arrangements to retrieve the diary card.

Visit 5 (5 months [+14 days] after Visit 4): Collection of Safety Information and Vaccination

- 1) If the diary card information from D0 to D07 (DC4) has not yet been obtained, obtain it at this time. Collect and review the pages of the diary card with the parent / guardian, including any AEs, medications, or therapy that occurred since vaccination. If an SAE, including an AESI, has occurred, follow the instructions in [Section 10](#) for reporting it.
- 2) Review the subject's relevant health history with parent / guardian, including any AEs, medications, or therapy that occurred since vaccination.
- 3) Review warnings and precautions to vaccinations.
- 4) Review contraindications to subsequent vaccinations.
- 5) Review conditions for withdrawal.
- 6) Contact IRT system for dose number for all vaccines to be given.
- 7) Administer the appropriate study vaccine per Operating Guidelines. Each vaccine should be administered in an assigned location and documented appropriately:
  - Meningococcal vaccine: inject IM into the anterolateral area of the thigh (preferably the right thigh).a,b
  - Prevnar 13®: inject IM into the anterolateral thigh (preferably the left thigh).a
  - M-M-R®II inject SC into the outer aspect of the upper arm (preferably the left arm)
  - Hexacima®: inject IM into the anterolateral area of the upper thigh (preferably the left thigh)
- 8) Keep the subject under observation for 30 minutes and record any AE in the source document.
- 9) Give the parent / guardian a diary card (DC5).
- 10) Remind the parent / guardian to expect a telephone call 8 days after Visit 5 and to bring back the diary card when they return for Visit 6 at a specified date and time.
- 11) Remind the parent / guardian to notify the site in case of an SAE.
- 12) Complete the relevant CRFs for this visit.

---

a The only other vaccine that can be administered with the meningococcal vaccine in the right thigh is ENGERIX-B®. Do not administer Pentaxim® or PREVNAR-13® in the right thigh.

b Multiple injections given in the same extremity should be separated as far as possible preferably 2.54 cm to 3.81 cm apart with a minimum of 2.54 cm. Keep the subject under observation for 30 minutes and record any AR in the source document.

Telephone Call 4 (Group 1) (8 [+2] days after Visit 5) / Telephone Call 5 (Group 2) (8 [+2] days after Visit 5)

Refer to steps in Telephone Call 1.

Visit 6 (30 [+14 days] days after Visit 5): Collection of Safety Information, Blood Sampling, and Trial Termination

- 1) If the diary card information from D0 to D07 (DC5) has not yet been obtained, obtain it at this time. Collect and review the pages of the diary card with the parent / guardian, including any AEs, medications, or therapy that occurred since vaccination. If an SAE, including an AESI, has occurred, follow the instructions in [Section 10](#) for reporting it.
- 2) Review temporary contraindications to blood sampling
- 3) Collect 6-mL blood sample (BL0003) (see [Section 7.1](#) for detailed instructions regarding the handling of blood samples).
- 4) Remind the parent / guardian to notify the site in case of an SAE.
- 5) Complete the trial termination record.

